6.5.3 Baseline/Randomization Visit

The baseline evaluations must be performed within 30 days of the Screening visit.

1. Medical History
2. Prior/Concomitant Medications
3. Physical Exam (symptom-driven)
4. Vital Signs including heart rate and sitting systolic/diastolic blood pressure
5. STAT Urine pregnancy test (for women of child-bearing potential)
6. Joint Examination – Physician's Assessment (including a swollen/tender joint count). *Note: The count will include 66 tender/64 swollen joints.*
 - *The ankle joint(s) on each limb will be counted as a single joint that includes the talo-tibial joint (also called the talo-crural joint), subtalar joint (also called talo-calcaneal joint), and inferior tibio-fibular joint.*
 - *The midfoot joints will not be evaluated for either tenderness or swelling.*
 - *The hip joints will not be evaluated for swelling.*
7. Randomization

IMPORTANT: Subjects with tender joints and/or swollen joints that are consistent with RA-like synovitis at the time of the Baseline/Randomization Visit should NOT be randomized or treated.

Note: Sites utilizing a central pharmacy may randomize subjects prior to the Baseline visit after initial eligibility at Screening has been confirmed, but if tender joints and/or swollen joints that are consistent with RA-like synovitis are noted at baseline, do NOT dispense the study medication to the subject.

8. Subject Questionnaires
 - Profile 29 v2.0
 - Epidemiologic Questionnaire
 - Dietary Assessment Questionnaire
 - Self-reported Joint Symptoms, including modified MDHAQ
 - Evaluate family member participation
9. Specimen collection for **real-time** core outcome testing (hsCRP, IgM-RF, Anti-CCP3) and serum for mechanistic studies.
10. Specimen collection for mechanistic studies: PBMC/plasma, RNA, and urine. *Note: DNA will be collected from subjects who consent to the optional specimen for shared epitope analysis.*
11. Dispense study therapy

Notes:

- *Female subjects cannot receive study therapy until eligibility can be confirmed via STAT urine pregnancy test.*
- *The first dose of study therapy will be given in clinic. The subject will be observed per institutional standards.*

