6.2. Demographic and Other Baseline Characteristics

Summary descriptive statistics for baseline and demographic characteristics will be reported for the ITT, mITT and PP samples by treatment group. Characteristics to be summarized include:

- Age
- Race (White, Black, Asian, Native Hawaiian or Other Pacific Islander, American Indian or Alaska Native, Other/Unknown)
- Hispanic ethnicity (Hispanic, Not Hispanic)
- Jewish ethnicity (Jewish, Not Jewish, Unknown)
- Sex (Male, Female)
- Body Mass Index (BMI)
- Recruitment Method (First Degree Relative (FDR), Clinic Patient, General Population)
- Participant Has a FDR with RA (Yes/No)
- Smoking Status (Smoker, Non-smoker)
 - For current smokers, baseline pack years at the current level will be computed as:
The average # cigarettes per currently smoked * the average # years at this level
- Baseline Cigar Use (Yes/No)
 - Cigar Users: Average Cigars per Day
 - Cigar Users: Number of Years Used Cigars
- Baseline Tobacco Pipe Use (Yes/No)
 - Tobacco Pipe Users: Average Bowls per Day
 - Tobacco Pipe Users: Number of Years Used Pipes
- Baseline Chewing Tobacco or Snuff Use (Yes/No)
 - Chewing Tobacco or Snuff Users: Average Wads per Day

Autoimmunity Centers of Excellence
Statistical Analysis Plan – ARA08 StopRA

- Chewing Tobacco or Snuff Users: Number of Years Used Chewing Tobacco or Snuff
- Baseline Electronic Cigarettes Use (Yes/No)
 - Electronic Cigarettes Users: Electronic Cigarette Use Frequency (\leq 1 Day a Week, 2-4 Days a Week, \geq 5 Days a Week)
 - Electronic Cigarette Users: Number of Years Used Electronic Cigarettes
- Baseline Anti-CCP3 (units)
- Baseline Anti-CCP3 Positivity (Negative ($<$ Upper Limit of Normal (ULN), Low Positive (1.0 - $<$ 2.0 x ULN), Medium Positive (2.0 - $<$ 3.0 x ULN), High Positive (\geq 3.0 x ULN))
- Baseline IgM-RF (U/mL)
- Baseline IgM-RF Positivity (Negative ($<$ Upper Limit of Normal (ULN), Low Positive (1.0 - $<$ 2.0 x ULN), Medium Positive (2.0 - $<$ 3.0 x ULN), High Positive (\geq 3.0 x ULN))
- Baseline hs-CRP (mg/L)
- Baseline hs-CRP Positivity (\leq 3.0 mg/L, $>$ 3.0 mg/L)
- Baseline Shared Epitope (SE) Positivity (Negative on all epitopes and specific alleles (e.g. *0401, *0404, etc.), Positive on at least 1 epitope or specific allele)
- Baseline Shared Epitope Number of Positive Results (0, 1, 2, etc.)
- Baseline Pain Score
- Baseline Fatigue Score
- Baseline Morning Stiffness Duration
- Baseline Number of Tender Joints from Physician Joint Exam

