- Baseline Disease Activity Score (28 joints) – C reactive protein (DAS28CRP)
- Baseline Routine Assessment of Patient Index Data 3 (RAPID3)
- Baseline Simple Disease Activity Index (SDAI)
- Baseline Clinical Disease Activity Index (CDAI)
- Baseline Patient-reported Outcomes Measurement Information System (PROMIS) Profile 29 Physical Health Score
- Baseline PROMIS Profile 29 Mental Health Score
- Baseline PROMIS Profile 29 Social Health Score

A listing of the demographic and baseline characteristics of randomized participants by treatment arm will be prepared.

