Population Level Summary: At each planned clinic visit, the number, and percent of individuals with self-reported joint symptoms will be computed by treatment arm, and separately for those with and without a prior study-confirmed diagnosis of CL- RA. Among those with symptoms, mean, median, min and max # of affected joints will also be reported. Summary statistics will also be plotted over time to gain a better understanding of trends.	Analysis: At Week 52 and Month 36/EOS, Mann-Whitney U statistics will be used to compare joint counts between treatment arms, separately for those with and without a diagnosis of CL-RA. Because the distributional characteristics of these variables are unknown, we cannot prespecify the planned analysis strategy. However, in this population, it is reasonable to expect there will be excess # of participant visits where no joint symptoms are reported. If this is the case, it may appropriate to fit a longitudinal zero-inflated negative binomial model with the number of involved joints as the dependent variable and treatment arm as the primary fixed effect. Important additional fixed effects to consider would include prior CL-RA diagnosis at time of assessment (Y/N), study day (or visit), treatment period (on study drug vs off study drug), duration on study treatment, and interaction terms for treatment arm, prior CL-RA diagnosis, and study day (or visit). Heterogeneous random participant effects could be included in the model per the methods of Zhu et al [4], and relevant covariates included in the regression on the covariance matrix will be determined. T-tests for the maximum likelihood estimates of the model parameters could be used to determine the significance of the parameters to the model.
Note: Modeling will be exploratory and only initiated if descriptive analyses suggest interesting trends.	

8.3.7. Study Objective 8

Study Objective 8 is to explore underlying immune responses over time in the early natural history of RA development and in response to HCQ therapy through measurement of a variety of biomarkers. Endpoints will be laboratory test results from mechanistic specimens collected at specified clinic visits during the study.

Table 15: Estimands of Study Objective 8

Estimand Label	Biomarkers and immune response variables
Secondary 8.1	Levels of anti-CCP3 over time
Secondary 8.2	Levels of IgM-RF over time
Secondary 8.3	Levels of hsCRP over time

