Population Level Summary: At each planned clinic visit, the number, mean (SD), median, min, and max score will be computed by treatment arm, and separately for those with and without a prior study-confirmed diagnosis of CL- RA. Summary statistics will also be plotted over time to gain a better understanding of trends.	Analysis: At Week 52 and Month 36/EOS, Mann-Whitney U statistics will be used to compare scores between treatment arms, separately for those with and without a diagnosis of CL-RA. If data are consistent with a Gaussian distribution, the data may be analyzed using a repeated measure mixed regression model with the scale score variable at each visit as the dependent variable and treatment arms as the primary fixed effect. Important additional fixed effects to consider would include prior CL-RA diagnosis at time of assessment (Y/N), study day (or visit), treatment period (on study drug vs off study drug), duration on study treatment, and interaction terms for treatment arm, prior CL-RA diagnosis, and study day (or visit). Random participant effects may include random intercepts and/or slopes for each participant
Note: Modeling will be exploratory and only initiated if descriptive analyses suggest interesting trends.	

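### The SAP's committed tests of joint counts, disease activity and PROMIS scores do not use the collected baseline value, which loses precision wherever baseline predicts follow-up

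*SAP*

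**What the plan says.** SAP 8.4.2 (Table 17) covers DAS28-CRP, CDAI, RAPID-3 and three PROMIS scores: "At Week 52 and Month 36/EOS, Mann-Whitney U statistics will be used to compare scores between treatment arms", and it does so "separately for those with and without a diagnosis of CL-RA". SAP 8.3.6 (Table 14, six self-reported joint counts) and 8.4.1 (Table 16, physician tender and swollen counts) share this commitment: "At Week 52 and Month 36/EOS, Mann-Whitney U statistics will be used to compare joint counts between treatment arms", with the same split by diagnosis. Neither a baseline term nor change from baseline appears in any of the three.

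Longitudinal models are described in all three tables, but under the condition "Modeling will be exploratory and only initiated if descriptive analyses suggest interesting trends". The fixed effects suggested for them are diagnosis, time, treatment period, duration on treatment and interactions. The baseline value is not among them.

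The baseline data exist. Protocol 6.5.3 schedules, at the Baseline visit, "Self-reported Joint Symptoms, including modified MDHAQ", the PROMIS profile, the joint examination and hsCRP. SAP 6.2 already summarises baseline DAS28-CRP, RAPID-3, CDAI, the PROMIS scores and "Baseline Number of Tender Joints from Physician Joint Exam". SAP 8.3.5 lists baseline self-reported joint pain, stiffness and swelling as candidate risk factors.

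The protocol planned something else for these endpoints. Section 8.3.1.2 commits to random regression models with a subject-level slope and intercept, Section 3.3.1 starts the first trend period at Baseline, and Section 8.5.4 allows ANCOVA as a sensitivity analysis. SAP Section 12 records only two departures from the protocol: the per-protocol repeats and the family-clustering analyses.

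**The concern.** A raw follow-up comparison leaves stable differences between participants in the noise. Recruits come from rheumatology clinics, health fairs and families of patients, and Protocol 4.3.3 says the clinic recruits are typically tested because of musculoskeletal pain. Some spread in symptoms before treatment is therefore plausible. Minimisation balances smoking, site and recruitment route, not symptom scores.

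At stake is how much these comparisons can show about symptoms, function and disease activity. They are run in small subsets, so precision that can be recovered from data already in hand is worth having. There is also a reporting matter: Protocol 8.5.5 says major changes will be noted in the SAP, and turning a committed longitudinal analysis into an optional one is not noted in Section 12.

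**Working it through.** **Inputs from the documents.** 144 randomised (Interim SAP 5.2.2.1); 20% loss per arm (Interim SAP Appendix 8.1); planning risk of CL-RA at 36 months of 50% on placebo and 25% on HCQ (Protocol 8.1); two-sided tests with 95% intervals (Protocol 8.3.1.2).

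**Assumptions, not in the documents.** Baseline-to-follow-up correlation r from 0 to 0.7; a shift of 0.5 SD between arms; the shape of the distributions.

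**1. The plan's own figure.** No power, SD or correlation is stated for these tests. The one figure to check is the primary design: 80 per arm, 50% v 25%, 90% power. On the logit scale the difference is ln 3 = 1.0986. SE² = 1/(80 × 0.5 × 0.5) + 1/(80 × 0.25 × 0.75) = 0.0500 + 0.0667 = 0.1167, so SE = 0.3416. Power = Φ(1.0986/0.3416 − 1.96) = Φ(1.256) = 89.6%. The stated 90% is reproduced.

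**2. Number of tests.** (6 + 2 + 6) variables × 2 visits × 2 strata = 56, none adjusted for baseline.

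**3. Stratum sizes at Month 36.** 144 × 0.8 / 2 = 57.6 per arm. Without CL-RA: 57.6 × 0.50 = 28.8 (placebo) and 57.6 × 0.75 = 43.2 (HCQ). With CL-RA: 28.8 and 14.4. The simulations use 29 v 43 and 29 v 14.

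**4. Variance after linear adjustment.** The ratio to the unadjusted variance is 1 − r²: 0.91, 0.75 and 0.51 at r = 0.3, 0.5 and 0.7. This is equivalent to 1.10, 1.33 and 1.96 times the sample.

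**5. Simulated power (%),** 3,000 trials per cell, 0.5 SD shift. The rank-adjusted test ranks outcome and baseline, takes residuals from regressing one set of ranks on the other, and compares them by arm. Zero-heavy counts are floor(max(0, e^z − 1)) of a normal z, so r is on the underlying scale and Φ(ln 2), about 76%, of unshifted values are zero.

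| Stratum, data | Test | r = 0 | 0.3 | 0.5 | 0.7 |
|---|---|---|---|---|---|
| No CL-RA, normal | Mann-Whitney | 53.1 | 52.4 | 52.2 | 52.2 |
| | Rank-adjusted | 53.0 | 55.9 | 63.4 | 76.6 |
| No CL-RA, zero-heavy | Mann-Whitney | 37.8 | 36.2 | 37.2 | 35.6 |
| | Rank-adjusted | 37.5 | 39.2 | 41.3 | 44.8 |
| | Plain ANCOVA | 23.4 | 23.7 | 26.5 | 34.7 |
| CL-RA, normal | Mann-Whitney | 31.5 | 29.9 | 29.7 | 29.5 |
| | Rank-adjusted | 32.0 | 33.9 | 37.6 | 48.6 |

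Monte Carlo standard error is at most √(0.25/3000) = 0.9 points. With no shift (29 v 43), every method rejected in 4.0% to 5.1% of trials.

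**6. Where nothing can be gained.** RA-like synovitis at Screening or Baseline bars entry (Protocol 6.5.2, 6.5.3). The physician swollen count is therefore zero at entry and carries no information as a covariate.

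**The case against.** The strongest case is that Mann-Whitney is valid here and was chosen for a stated reason: SAP 8.3.6 and 8.4.1 say the distributions of the counts are unknown and expect many zeros. Secondary p-values are descriptive (SAP 8.1.4), Tables 16 and 17 sit under exploratory endpoints, and the DSMB recommended stopping for futility (SAP 5.4). All of this stands. It limits the importance of the point but does not remove the loss of precision.

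It is also fair that r may be low. Participants enter without arthritis, and Protocol 6.5.3 bars tender or swollen joints consistent with RA-like synovitis at Baseline. That may compress tender counts, CDAI and DAS28-CRP at entry. With no correlation in the documents, the gain may be close to nil for some measures.

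Three stronger readings are tempting and are not supported:

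- A reader might infer that the trial never planned to use baseline for these endpoints. The protocol's committed random regression covers a period that starts at Baseline; the gap is in the SAP's committed tests.
- A reader might infer that the optional models lose baseline too. In Table 17 the response is the score at each visit, with random participant effects possible, and Baseline is a scheduled clinic visit. Baseline can enter as part of the response.
- A reader might quote power for whole arms. At 58 v 58 with normal scores, Mann-Whitney gives 73-75% and the rank-adjusted test 78%, 84% and 94% at r = 0.3, 0.5 and 0.7. The SAP splits by diagnosis, and 8 of the 14 variables are joint counts, so those figures do not describe the planned tests.

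**Conclusion.** The point holds for the SAP's committed tests in Tables 14, 16 and 17. It matters mainly for the six Table 17 scores. In the Month 36 stratum without CL-RA, adjustment would raise power from about 52-53% to between 56% and 77% for r from 0.3 to 0.7. For zero-heavy self-reported and tender counts the corresponding rise is from 36-38% to 39-45%. For physician swollen joints, and for any measure with r = 0, there is no gain.

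These figures rest on an assumed 0.5 SD shift, assumed correlations and distributions, and strata built from planning risks and planned loss. The strata are not observed numbers, and Week 52 was not simulated by stratum.

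The loss is one of efficiency; the tests hold their level under the simulated null. Nor would adjustment make the stratum comparisons fully randomised ones. CL-RA status arises after randomisation, and a baseline covariate does not remove the selection that the split introduces. The primary analysis is not touched.

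**What to change.** 1. In Table 17, and in Tables 14 and 16 for the self-reported and tender counts, make the Week 52 and Month 36/EOS comparison a rank-based ANCOVA with the baseline value of the same measure as covariate. Keep Mann-Whitney as a check and report both. Leave the physician swollen count as it is.
2. Do not use plain ANCOVA for the counts; in the zero-heavy simulation without CL-RA it fell below Mann-Whitney at every r.
3. In the optional longitudinal models, use baseline either as part of the response or as a covariate with the Baseline visit removed from the response, not both.
4. State in SAP Section 12 that the random regression models of Protocol 8.3.1.2 were made optional. Date this and the change of test, because SAP 5.4 says assignments are unmasked before database lock.

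The cost is SAP wording and a little programming, with no new data. Participants without a baseline value would drop out of the adjusted test but stay in the Mann-Whitney check; the documents do not say how many there are.

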9. SAFETY EVALUATIONS

9.1. Overview of Safety Analysis Methods

All safety analyses will be carried out using the Safety Population defined in Section 5.1 unless otherwise noted. Missing safety information will not be imputed. These analyses will not be stratified by site.

Safety will be analyzed in both treatment arms through the reporting of adverse events (AEs), vital signs, physical examination findings, and changes in routine laboratory values.

Listings will be prepared for all safety measurements. All listings will be sorted in order of treatment, participant identifier (ID), and time of assessment (e.g., visit, time, and/or event).

9.2. Extent of Exposure

Duration of exposure will be defined as the last dose date – first dose date + 1. Descriptive statistics will be presented by treatment arm.

9.3. Adverse Events

All AEs will be classified by system organ class (SOC) and preferred term, according to a standardized thesaurus (Medical Dictionary for Regulatory Activities [MedDRA] version 23.0). The severity of AEs will be classified using the National Cancer Institute's (NCI's) Common Toxicity Criteria for Adverse Events (CTCAE) version 4.0. Each AE is entered on the electronic case report form (CRF) once at the highest severity. As such, no additional data manipulation is needed to identify events.

AEs will be collected starting at consent for Grade 2 or higher AEs related to a study-mandated procedure, treatment, or change in treatment, and will be collected starting from the first dose of study treatment through Month 18 or until 30 days after the participant prematurely terminates from the study, whichever occurs first. SAEs are collected for participants throughout the duration of their participation in the study. Treatment-emergent AEs will be identified as those with an onset date on or after the first dose of study medication. If the start of the AE in relation to the start of study medication cannot be established (e.g., the start date for the AE is missing), then the AE will be considered treatment-emergent. If an abnormal laboratory finding is reported as an AE on the first day of study drug (Day 1), these events will not be considered treatment emergent since these assessments occur prior to treatment initiation. All data tabulations will be of only treatment-emergent events while non-treatment-emergent AEs will be included in the listing of all AEs.

The frequency of AEs will be summarized by system organ class, preferred term, severity (grade), and relationship to study treatment. Relationship to study treatment, as determined by masked investigators, will be categorized as either treatment related (possibly, probably, or definitely related to study medication) or unrelated (unlikely related or unrelated). Similar analyses will be performed for SAEs. To account for differential duration of study participation among participants, the summaries will also include the event rate (i.e., number of events per person-time) in addition to the number and percent of events and participants experiencing events.

For the secondary safety endpoint of the proportion of participants in each arm experiencing a Grade 3 or higher AE according to the National Cancer Institute-Common Terminology Criteria for Adverse Events (NCI-CTCAE) system, the proportion of participants experiencing at least one event in each treatment group will be reported and the treatment groups compared based on Fisher's Exact Test.

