5.8 Treatment Discontinuation and Subject Withdrawal

5.8.1 Study Treatment Discontinuation

Study treatment will be discontinued permanently for any individual subject under the following conditions:

1. At any time during the study at the request of the subject or subject's guardian.
2. If investigators or NIAID determine that the subject's health, safety, and/or well-being are threatened.
3. If the subject is administered any of the medications outlined in Section 5.6, *Prohibited Medications*, whether the medication is prescribed by a study site investigator or an outside physician. Study drug should be discontinued at the time the study team becomes aware that the subject has started prohibited medications.
4. Study treatment will be discontinued for any subject who experiences any of the following:
 - a. Pregnancy
 - b. Development of clinically-apparent RA via the 2010 ACR/EULAR Criteria (defined as a score ≥ 6 , OR findings consistent with RA-like synovitis paired with ≥ 1 erosion(s) identified by x-ray) at a single study visit.
 - c. An AE of Grade 3 or higher by the National Cancer Institute-Common Terminology Criteria for Adverse Events (NCI-CTCAE) that is probably, possibly, or definitely related to HCQ.
 - d. Retinal disease consistent with HCQ toxicity as described in Section 1.4.2, *Known and Potential Risks of Hydroxychloroquine*.
 - e. Any allergic reaction attributed to study drug (see Section 1.4.2.2, *Additional Toxicities*)
 - f. Any of the following persistent lab abnormalities:

Note: Abnormal lab values meeting a criterion noted below should be confirmed within 4 weeks, prior to discontinuation.

 - i. Serum creatinine clearance < 50 ml/min;
 - ii. ALT or AST $\geq 3.5x$ the upper limit of normal (ULN);
 - iii. WBC $\leq 2.5 \times 10^9/L$;

- iv. Platelet count < 75 x10⁹/L;
- v. Hemoglobin < 10 g/dL;
- vi. ANC < 1.5 x10⁹/L

Subjects who discontinue protocol-specified treatment requirements will be treated as medically indicated according to physician discretion.

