Research Blood Draw (mL)	NA	66	10	10	10	66	66	NA
Visit Draw Total (mL)	NA	66	10	10	10	66	66	NA
General Assessments								
Demographics						X	X	
Concomitant Medications			X	X	X	X	X	X
Physical Exam ²⁹			X	X	X	X	X	X
Vital Signs including heart rate & sitting systolic/diastolic blood pressure				X				X
Vital Signs including heart rate, sitting systolic/diastolic blood pressure, weight, & waist circumference						X	X	
AE/SAE Assessment			X ³⁰	X ³⁰	X ³⁰	X ³⁰		X ³⁰
Profile 29 v2.0			X			X		X
Epidemiologic Questionnaire				X ³¹		X ³¹	X	
Dietary Assessment Questionnaire						X ³¹	X	
Self-Reported Joint Symptoms, including modified MDHAQ			X	X	X	X	X	X
Evaluate family member participation ³²			X	X	X	X	X	X
Pregnancy Status Check				X ³¹	X ³¹	X ³¹	X ³¹	X ³¹
Follow-up Telephone Assessments ³³		X ³¹						
Annual Phone Call for Withdrawn Subjects					X ³⁴		X ³⁴	
Disease Status								
Joint Examination – Physician’s Assessment: 64 /66 tender/swollen joint count ³⁵				X ³⁶	X ³⁶	X ³⁶	X	X ³⁶
Real Time Core Outcome Testing (hsCRP, IgM-RF, Anti-CCP3) & serum ³⁷			X ³⁸				X ³⁹	
Future Core Outcome Testing (hsCRP, IgM-RF, Anti-CCP3) & serum				X ³¹	X ³¹	X ³¹		X
2010 ACR/EULAR Criteria ⁴⁰			X					
X-ray as needed ⁴¹			X ⁴¹					
Clinical Laboratory Assessments								
Hematologies: Hemoglobin, Hematocrit, WBC (with differential), & Platelet count								X ⁴²
Chemistries: Serum creatinine, ALT, & AST								X ⁴²
STAT Urine Pregnancy Test			X ⁴¹					
Required Mechanistic Specimens ³¹								
PBMC/Plasma/DNA, RNA, Urine ⁴³			X ⁴⁴			X ³¹	X	
HCQ Level ⁴⁵						X ⁴⁶	X ⁴⁶	

²⁸ See protocol section 6.5.9, *Evaluations Triggered by a Swollen Joint*, for additional details.

²⁹ Physical Exam: Full PE at Screen, Week 52, Time of Diagnosis and Month 36/Early Termination. Symptom-driven PE at all other clinic visits.

³⁰ Non-serious adverse events will not be collected after Month 18. SAEs will be collected for the duration of the study.

³¹ These procedures will be conducted if the subject **has not** been previously diagnosed with clinically-apparent RA.

³² All participants should complete the “Participation of First Degree Relatives” questionnaire. If the subject consents to linking his/her information with a participating family members, please follow the Process for Linking First Degree Relatives in the Manual of Operations.

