7.3.2 Collection Period

AEs of NCI-CTCAE Grade 2 and above will be collected from the time the subject signs the main clinical trial informed consent until he/she initiates study intervention or until he/she is determined to be ineligible to receive study intervention, if the investigator determines that the AE is related to a study-mandated procedure, treatment, or change in treatment.

Regardless of whether the above is applicable, for all participants, AEs of NCI-CTCAE Grade 2 and above will be collected from the time of initiation of study intervention (i.e., the administration of the first dose of study drug (HCQ/placebo), as defined in Section 6.5.3, *Baseline/Randomization Visit*), until Month 18 or until 30 days after he/she prematurely withdraws (without withdrawing consent) or is withdrawn from the study.

Serious adverse events will be collected throughout the duration of the subject’s participation in the study.

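### SAP 9.3 gives treatment-emergent a start but no end, so no adverse event table isolates events on study drug

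*SAP*

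**What the plan says.** SAP 9.3 defines the flag by its start only: "Treatment-emergent AEs will be identified as those with an onset date on or after the first dose of study medication". The one exception is an abnormal laboratory finding reported on Day 1, which is not counted. The same section then says "All data tabulations will be of only treatment-emergent events"; other events appear only in a listing. For the secondary safety endpoint, Grade 3 or higher AEs, "the proportion of participants experiencing at least one event in each treatment group will be reported and the treatment groups compared based on Fisher's Exact", and no time window is given.

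The collection periods set the practical limits. SAP 9.3 has AEs collected "starting from the first dose of study treatment through Month 18 or until 30 days after the participant prematurely terminates", while "SAEs are collected for participants throughout the duration of their participation in the study". The protocol agrees: section 7.3.2 has "Serious adverse events will be collected throughout the duration of the subject’s participation in the study", and the footnote to Table 6.2 (Schedule of Events, Follow-Up) says "Non-serious adverse events will not be collected after Month 18. SAEs will be collected for the duration of the study".

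Study drug is given for 12 months, with 24 further months of follow-up (Protocol 1.2). It stops earlier if clinically-apparent RA (CL-RA) develops. From then on, "Subjects who discontinue protocol-specified treatment requirements will be treated as medically indicated according to physician discretion" (Protocol 5.8.1), and participants are encouraged to attend all remaining visits (Protocol 6.5.5.6 and 6.5.10).

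**The concern.** Secondary objective 1 is the safety of a 12-month HCQ course. With no end to the flag, an SAE at Month 35, 23 months after a completed course, enters the treatment-emergent tables together with one at Month 3. An event in a participant who has moved to another RA drug, or in a placebo participant taking off-study HCQ, is counted to the randomised arm. If HCQ raises event rates only while it is taken, off-drug time adds background events to both arms and shrinks the ratio between them.

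The documents draw this line elsewhere. SAP 6.3 has a post-treatment class for medications that start after the last dose. The DSMB trigger in Protocol 5.8.3 counts SAEs in the 12-month treatment period only. The primary efficacy analysis censors at off-study HCQ and at prohibited medication (SAP Table 5, Policy 1). The AE analysis has no such split.

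**Working it through.** The plan states no figure for this point, so there is none to reproduce. The steps below size the off-drug share and illustrate its effect.

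**Inputs**
- Drug 12 months, total 36 months (Protocol 1.2).
- Non-serious AEs to Month 18, SAEs to Month 36 (SAP 9.3; Protocol 7.3.2).
- Design RA risk at 3 years: 50% placebo, 25% HCQ; hazards 0.231 and 0.096 per year (Protocol 8.1).
- 144 randomised (interim SAP 5.2.2.1), taken as 72 per arm.
- Assumptions, because the documents give no AE rates: HCQ doubles the event rate on drug, has no effect off drug, and the background rate is constant.

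**1. Off-drug share for a participant who completes treatment**
- Non-serious AEs: 18 − 12 = 6 months; 6/18 = 33%.
- SAEs: 36 − 12 = 24 months; 24/36 = 67%.

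A participant who stops drug early has a longer off-drug window. These are planned maxima: SAP 5.4 reports a DSMB recommendation to stop early, so some participants may not have reached Month 36.

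**2. Diluted rate ratio, full 12 months on drug**
- To Month 18: (2 × 12 + 6)/18 = 1.67.
- To Month 36: (2 × 12 + 24)/36 = 1.33.

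**3. The same, allowing drug to stop at CL-RA at the design hazard**

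Mean on-drug time in years is (1 − exp(−λ))/λ: 0.953 on HCQ and 0.893 on placebo.
- To Month 18: (2 × 0.953 + 0.547)/1.5 = 1.64.
- To Month 36: (2 × 0.953 + 2.047)/3 = 1.32.

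**4. Effect on the Fisher test (illustration)**

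Assume on-drug Grade 3 or higher risks of 20% on HCQ and 5% on placebo, and an off-drug risk r per year that is equal in both arms. For six off-drug months q = 1 − (1 − r)^0.5, and the combined risk is 1 − (1 − p)(1 − q). Exact power of the two-sided 5% test, 72 per arm:

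| Window | HCQ vs placebo | Difference | Power |
|---|---|---|---|
| On drug only | 20.0% vs 5.0% | 15.0 points | 74% |
| Plus 6 months, r = 3% | 21.2% vs 6.4% | 14.8 points | 68% |
| Plus 6 months, r = 20% | 28.4% vs 15.0% | 13.4 points | 43% |

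With 24 off-drug months the same range of r gives 54% to 17%. That is an extreme for this endpoint, because non-serious Grade 3 events stop at Month 18 and only serious ones run on. The endpoint therefore mixes two windows, neither tied to the last dose.

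**5. Time after CL-RA, under the design risks only**

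Mean time after diagnosis over 3 years is 3 − (1 − S)/λ.
- Placebo: 3 − 0.50/0.231 = 0.84 years, or 28% of 36 months.
- HCQ: 3 − 0.25/0.0959 = 0.39 years, or 13%.

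This is time in which other RA drugs could be taken, assuming full follow-up. No document says what share of participants would start them.

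**The case against.** Comparing all events after the start of randomised treatment is a legitimate choice. The objective is the safety of a course, not only of time on drug, and the full window does not condition on anything that happens after randomisation. An on-treatment window does: drug stops at CL-RA, which is the efficacy outcome. At the design hazards HCQ would have 0.953/0.893 = 1.07 times the on-drug time of placebo. The protocol also describes retinopathy appearing after HCQ was stopped (1.4.2.1), so later events belong in the report. This stands, and it is why the planned tables should stay.

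The plan also has partial safeguards. AE and SAE tables are split into related and unrelated by masked investigators, listings are ordered by time, and the laboratory change tables cover only Weeks 24 and 52. Protocol 8.3.2 calls all safety comparisons exploratory. These points lower the stakes. They do not supply the missing contrast: attribution is a judgement that the Fisher test does not use, and the planned event rates adjust for study participation, not drug exposure.

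A reader might infer that the plan hides HCQ harm. The documents do not show that. They give no event rates, and under the assumptions of steps 2 and 3 the absolute excess of HCQ events stays in the counts; it is the ratio that shrinks. The ratios in those steps are rate ratios and do not measure the Fisher test, which compares proportions.

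**Conclusion.** The gap is real and modest. The definition has no end, all AE tabulations depend on it, and no AE table separates events on study drug from later ones. In a participant who completes the course, a third of the non-serious AE window and two thirds of the SAE window are off drug. The relative on-drug contrast is pulled toward the null: a true doubling would appear as 1.64 to 1.67 to Month 18 and 1.32 to 1.33 to Month 36, given a constant background rate and no off-drug effect. The actual size is unknown.

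Two stronger readings are not supported. The 24-month tail applies to SAEs only; other AEs stop at Month 18. A bias favouring HCQ, through more RA treatment on placebo, needs RA rates to differ between arms. The 28% versus 13% in step 5 rests on the design risks, while SAP 5.4 reports evidence of futility at the interim analysis. If RA rates are similar, the dilution is largely non-differential.

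**What to change.** Keep the planned whole-follow-up tables and Fisher test, and add to SAP 9.3:

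- A prespecified on-treatment window, from first dose to last dose plus an interval that the sponsor justifies. The protocol's 30-day period follows withdrawal from the study, not the last dose, so it does not settle that interval.
- The Grade 3 or higher comparison and the AE and SAE tables repeated on that window, with rates per on-treatment person-time.
- A separate post-treatment tabulation of later events, split by onset before or after the start of another RA drug or off-study HCQ.

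The AE, dosing and medication dates are already collected, so the cost is SAP wording and one more set of tables. The downside is fewer events per table. The on-treatment window would also be slightly shorter on placebo if more placebo participants stop drug at CL-RA, so the rates should be read alongside the proportions.
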